10.0 Study Withdrawal/Discontinuation

Patients can be withdrawn from study participation in the following circumstances:

- The investigator decides that the patient should be withdrawn for safety considerations.
- There is a significant protocol violation in the judgment of the PI.

The reason and date of every withdrawal will be recorded in the patient study records. Follow-up will be performed for all patients who discontinue due to an adverse event or any other safety parameter. Follow-up will also be performed for all patients who end participation in the protocol for another reason, but who also have an adverse event or other safety parameter that could have led to discontinuation. Follow-up will be conducted until the condition has resolved, until diagnosis of the adverse event or safety parameter is deemed chronic and stable, or as long as clinically appropriate. This follow-up will be documented in the patient study record as well.

11.0 Statistical Considerations

Power calculation.

In a prior cluster-randomized cluster-crossover trial in the same ICU,⁵¹ 880 mechanically ventilated adults were enrolled per year (73.3 per month), with a median of 22 VFDs [IQR 0-25 VFDs] and an intra-cluster intra-period correlation of 0.01. During the planned 36-month PILOT trial, we estimate 2,640 mechanically ventilated adults will be admitted to the study ICU, of whom 390 will be enrolled during washout periods and excluded from the primary analysis and 2,250 will be included in the primary analysis. With a total enrollment of 2,250 patients, a standard deviation in the primary outcome of VFDs of 11.4 days, and a two-sided alpha of 0.05, ***the PILOT trial will have 92 percent statistical power to detect an absolute difference between groups in VFDs of 2.0 days*** (similar to the numerical difference in VFDs between SpO₂ target groups reported in prior studies^{29,30}).

Primary analysis of the Primary Outcome.

The primary analysis will be an intention-to-treat comparison of the primary outcome of VFDs between the higher, intermediate, and lower SpO₂ target groups among all patients enrolled in the trial except [1] those admitted during one of the 7-day washout periods and [2] those with a laboratory-confirmed diagnosis of Coronavirus disease 2019 (COVID-19). We will use a proportional odds model with independent covariates of group assignment (higher, intermediate, or lower SpO₂ target) and time. Time (in days) will be treated as a continuous variable with values ranging from 1 (first day of enrollment) to 1,097 (final day of enrollment) and will be analyzed using restricted cubic splines with multiple knots to allow for non-linearity resulting from seasonality or secular trends. For the purposes of declaring a statistically significant

difference between groups in the primary endpoint, we will consider the conditional effect from the proportional odds model and a two-sided P value of 0.05. In addition to the overall comparison of the three study groups, we will perform pair-wise comparisons between the lower and intermediate groups, lower and higher groups, and intermediate and higher groups using the same statistical approach.

Sensitivity Analyses of the Primary Outcome

- We will repeat the primary analysis using alternative statistical approaches to comparing the VFDs outcome between groups. These statistical approaches will include:
 - zero-inflated Poisson regression;
 - zero-inflated negative binomial regression;
 - global rank scale analysis (see Supplementary Appendix); and
 - Fine and Gray competing risk regression in which extubation from invasive mechanical ventilation is the event of interest and mortality is a competing event.
- We will repeat the primary analysis with adjustment for pre-specified baseline covariates.
- We will repeat the primary analysis replacing the continuous covariate of time with a categorical covariate of season defined as: winter (January, February, March); spring (April, May, June); summer (July, August, September); and fall (October, November, December).
- We will repeat the primary analysis among all patients enrolled in the trial, including [1] patients initiated on invasive mechanical ventilation in a study location during one of the pre-specified 7-day washout periods and [2] patients with a diagnosis of COVID-19 (estimated sample size of 3,000 patients).

Analysis of Effect Modification for the Primary Outcome.

We will examine whether pre-specified baseline variables modify the effect of study group on the primary outcome using formal tests of statistical interaction in a proportional odds model. Independent variables will include study group assignment, the potential effect modifier of interest, and the interaction between the two (e.g., study group * presence of sepsis or septic shock) and time. Significance will be determined by the P value for the interaction term, with values less than 0.10 considered to suggest a potential interaction and values less than 0.05 considered to confirm an interaction.

We will examine whether the following baseline variables modify the effect of study group on the primary outcome:

- Age (continuous variable);
- Race and ethnicity (Hispanic, Non-Hispanic Black, Non-Hispanic White, Other);
- Source of admission to the ICU (ED, hospital ward, another ICU in the study hospital, operating room, outside hospital);

- Duration of invasive mechanical ventilation prior to enrollment (0 minutes; 1 to 360 minutes; >360 minutes);
- Chronic comorbidities (categories are not mutually exclusive)
 - Receipt of supplemental oxygen at place of residence prior to hospital admission (yes, no);
 - Coronary artery disease or heart failure with reduced ejection fraction (yes, no);
- Acute diagnoses at enrollment (categories are not mutually exclusive)
 - cardiac arrest (yes, no);
 - acute myocardial infarction (yes, no);
 - sepsis or septic shock (yes, no);
 - acute respiratory distress syndrome (yes, no);
- Receipt of vasopressors at enrollment (yes, no);
- Non-respiratory SOFA score at enrollment (continuous variable);
- Time period (before the COVID-19 pandemic [July 2018 - December 2019], during the COVID-19 pandemic [January 2020 – August 2021]).

Analysis of the Secondary Outcome

The sole pre-specified secondary outcome of 28-day in-hospital mortality will be compared between the three study groups in an intention-to-treat fashion in the primary analysis population using a logistic regression model with independent covariates of group assignment (higher, intermediate, or lower SpO₂ target) and time. We also will perform pair-wise comparisons between the lower and intermediate groups, lower and higher groups, and intermediate and higher groups using the same statistical approach.

Analysis of the Exploratory Outcomes

Each of the exploratory outcomes will be compared between groups in an intention-to-treat fashion in the primary analysis population. Continuous outcomes will be compared between groups using a proportional odds model with independent covariates of group assignment (higher, intermediate, or lower SpO₂ target) and time. Categorical outcomes will be compared between groups using a logistic regression model with independent covariates of group assignment (higher, intermediate, or lower SpO₂ target) and time.

Corrections for multiple testing

We have pre-specified a single primary outcome and a single secondary outcome. Consistent with recommendations of the Food and Drug Administration and the European Medicines Association, each will be tested using a two-sided p-value with a significance level of 0.05. For all other analyses, emphasis will be placed on the estimate of effect size with 95% confidence intervals, as recommended by the

International Committee of Medical Journal Editors, and no corrections for multiple comparisons will be performed.

Handling of missing data

The primary outcome of VFDs is not anticipated to be missing for any patients. Missing data will not be imputed for the primary outcome or any secondary or exploratory outcomes. In adjusted analyses, missing data for covariates will be imputed using multiple imputations.

Interim Analysis

We will plan for the DSMB to conduct a single interim analysis for efficacy and safety at the anticipated halfway point of the trial. The interim analysis will include patients enrolled during the first 18 months of the trial. The stopping boundary for efficacy will be met if the P value for the difference between groups is <0.001 using a proportional odds model with independent covariates of group assignment (higher, intermediate, or lower SpO₂ target) and time with regard to the primary outcome of VFDs. Use of the conservative Haybittle-Peto boundary ($P < 0.001$) will allow the final analysis to be performed using an unchanged level of significance ($P = 0.05$). Given the minimal risk nature of the study and current use of all SpO₂ target as a part of usual care, there will be no stopping boundary for futility. The DSMB will reserve the right to stop the trial at any point, request additional data or interim analyses, or request modifications of the study protocol as required to protect patient safety.

If the 18-month interim analysis reveals an enrollment indicative of $<80\%$ statistical power at completion, we will ask the DSMB to approve extending enrollment of the study to ensure the trial is not underpowered to detect the planned difference between groups in the primary outcome.

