2. Throughout the study period, audit in-person at least every fourteen (14) days to confirm that copies of the most recent IRB-approved information sheet are available in a brochure holder on the display table in the medical ICU family waiting room. At least twice a year, take a photograph of the most recent IRB-approved information sheets in a brochure holder on the display table in the medical ICU family waiting room. Store the photographs with the date and time that they were taken electronically in the study files and in hard copy in the study binder.
3. Throughout the study period, audit in-person at least every fourteen (14) days to confirm that additional copies of the information sheet are available in the physician and respiratory therapy offices to be provided to patients, families, or surrogates with questions or concerns about the study.
4. Record and complete a case report form in the study database detailing contact about the study between patients, families, and surrogates and study personnel.

6.6 Randomization:

During each two-month block of the study, the ICU will be assigned to either a higher SpO₂ target (target 98% and goal range 96-100%), an intermediate SpO₂ target (target 94% and goal range 92-96%), or a lower SpO₂ target (target 90% and goal range 88-92%). The order of study group assignments will be generated by computerized randomization using permuted blocks of 3 to minimize the impact of seasonal variation. The last 7 days of each two-month block will be a washout period during which the ICU will continue to target the assigned SpO₂ but new patients will not be included in the primary analysis. Assuming a duration of mechanical ventilation similar to that observed for mechanically ventilated patients admitted to the study ICU in a prior year (median 3 [IQR 3-5] days), a 7-day washout period will ensure that 98% patients do not experience a “crossover” from one assigned SpO₂ target to another.

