 - a. Receipt of supplemental oxygen at place of residence prior to hospital admission (yes, no);
 - b. Coronary artery disease or heart failure with reduced ejection fraction (yes, no);
6. Acute diagnoses at enrollment (categories are not mutually exclusive) [56]
 - a. cardiac arrest (yes, no);
 - b. acute myocardial infarction (yes, no);
 - c. sepsis or septic shock (yes, no);
 - d. acute respiratory distress syndrome (yes, no);
7. Receipt of vasopressors at enrollment (yes, no);
8. Non-respiratory SOFA score at enrollment;
9. Time period (before the COVID-19 pandemic [July 2018 - December 2019], during the COVID-19 pandemic [January 2020 – August 2021]).

Analysis of the Secondary Outcome

The sole pre-specified secondary outcome of 28-day in-hospital mortality will be compared between the three study groups in an intention-to-treat fashion in the main analysis population using a logistic regression model with independent covariates of group assignment (higher, intermediate, or lower SpO₂ target) and time. In addition to assessing for an overall group effect within the model, we will estimate the differences between each pair of SpO₂ targets by extracting 95% confidence intervals from the model.

Analysis of the Exploratory Outcomes

Each of the exploratory outcomes will be compared between groups in an intention-to-treat fashion in the main analysis population. Exploratory outcomes will be compared between study groups in a similar manner as for primary and secondary outcomes. A logistic model will be used for binary outcomes, a multinomial model for categorical outcomes, and a proportional odds model will be used for ordinal and continuous outcomes.

Trial Status

PILOT is an ongoing pragmatic trial comparing higher, intermediate, and lower SpO₂ targets for mechanically ventilated critically ill adults. Patient enrollment began on July 1, 2018 and is anticipated to conclude on August 31, 2021.

Ethics and dissemination

IRB Approval

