The sole prespecified secondary outcome of 28-day in-hospital mortality will be compared between the three study groups in an intention-to-treat fashion in the main analysis population using a logistic regression model with independent covariates of group assignment (higher, intermediate or lower SpO₂ target) and time. In addition to assessing for an overall group effect within the model, we will estimate the differences between each pair of SpO₂ targets by extracting 95% CIs from the model.

Analysis of the exploratory outcomes

Each of the exploratory outcomes will be compared between groups in an intention-to-treat fashion in the main analysis population. Exploratory outcomes will be compared between study groups in a similar manner as for primary and secondary outcomes. A logistic model will be used for binary outcomes, a multinomial model for categorical outcomes, and a proportional odds model will be used for ordinal and continuous outcomes.

Trial status

PILOT is an ongoing pragmatic trial comparing higher, intermediate and lower SpO₂ targets for mechanically ventilated critically ill adults. Patient enrolment began on 1 July 2018 and is anticipated to conclude on 31 August 2021.

Ethics and dissemination

IRB approval

The trial was approved by the IRB of Vanderbilt University Medical Center with a waiver of informed consent (IRB# 171272), details of which are provided in (online supplemental file 1, section 26). Participants who regain capacity to provide informed consent, or legally authorised surrogate decision-makers for those patients who do not regain the capacity to provide informed consent, are approached to provide informed consent for assessment of long-term outcomes as a part of the independently funded CO-PILOT study (R21AG063126).

Information for patients and families

An information sheet providing an IRB approved lay language summary of the study and containing the contact information for investigators (who remain available

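### Final comparisons of mortality and safety outcomes omit washout and COVID-19 patients, and the all-enrolled sensitivity analysis covers ventilator-free days only

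*Combined protocol and SAP*

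**What the plan says.** Protocol version 1.5, section 11.0 (Analysis of the Exploratory Outcomes) states: "Each of the exploratory outcomes will be compared between groups in an intention-to-treat fashion in the primary analysis population". The exploratory outcomes include the safety list in section 7.4: atrial and ventricular arrhythmia, cardiac arrest, pneumothorax or pneumomediastinum, ischemic stroke and myocardial infarction. The SAP, under Analysis of the Secondary Outcome, compares 28-day in-hospital mortality "in an intention-to-treat fashion in the main analysis population using a logistic regression model". It uses the same population for the exploratory outcomes.

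That population excludes washout admissions and laboratory-confirmed COVID-19. Washout patients are nevertheless treated under the trial. Protocol 6.6 says that in the last 7 days of each block "the ICU will continue to target the assigned SpO₂ but new patients will not be included in the primary analysis", and the power paragraph in 11.0 expects that "390 will be enrolled during washout periods and excluded from the primary analysis and 2,250 will be included in the primary analysis".

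Excluded patients return in one planned analysis, a repeat of the primary analysis of VFDs in everyone enrolled ("estimated sample size of 3,000 patients"). Neither the protocol nor the SAP plans a similar repeat for mortality or safety outcomes.

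**The concern.** The washout exclusion serves the efficacy contrast by limiting crossover between targets. It does not mean that these patients were unexposed. They are enrolled at the start of ventilation, which protocol 6.4 describes as the period of greatest risk of hyperoxia and hypoxia, and they are titrated to the assigned target.

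The trial runs under a waiver of consent argued on minimal risk. In addition, protocol 9.2 exempts death, cardiac arrest, arrhythmia and pneumothorax from routine adverse event recording, apart from events thought study-related or worse than expected. Its argument is that these events are tracked in all patients and analysed. Section 11.0 then leaves some enrolled patients out of every separate final comparison of those events. An imbalance in deaths among them would be visible only inside a composite. An imbalance in their arrests with recovery, strokes, infarctions or pneumothoraces would not be visible in any final comparison.

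**Working it through.** **1. The plan's counts.** Protocol 11.0 cites a prior trial in which "880 mechanically ventilated adults were enrolled per year (73.3 per month". Then 880 × 3 = 2,640 and 2,640 − 390 = 2,250, or 750 per group. The stated power also reproduces at 750 per group: 2.0 / (11.4 × √(2/750)) = 3.397; 3.397 − 1.960 = 1.437; Φ(1.437) = 0.925, against 92% stated. So 2,250 is a forecast with washout as its only exclusion.

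**2. Washout share.**
- By the plan's counts: 390 / 2,640 = 14.8%.
- By calendar: 18 blocks × 7 days = 126 days; 126 / 1,097 enrollment days = 11.5%.

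**3. Share with COVID-19 added.** 3,000 − 2,250 = 750, and 750 / 3,000 = 25.0%. The two totals have different bases: 3,000 is a separate estimate that includes COVID-19 patients and exceeds 2,640. In 3,000 patients, washout would account for 345 (11.5%) to 443 (14.8%). For the primary population still to be 2,250, the other 307 to 405 (10 to 14% of all enrolled) would have to be COVID-19 patients, a number given nowhere. With w the washout share and c an assumed COVID-19 share, independent of washout, the excluded share is 1 − (1 − w)(1 − c):

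| c | w = 11.5% | w = 14.8% |
|---|---|---|
| 0% | 11.5% | 14.8% |
| 5% | 15.9% | 19.0% |
| 10% | 20.3% | 23.3% |
| 12% | 22.1% | 25.0% |

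**4. Precision.** Assume a 5% event rate and equal groups. The standard error of a pairwise difference is √(2 × 0.05 × 0.95 / n): 1.13 points at n = 750 and 0.97 at n = 1,000. The ratio is 0.866, a 13% reduction.

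Now apply the plan's intra-period correlation of 0.01, which is quoted with the VFD figures and is only assumed to hold for safety events. The design effect is 1 + (m − 1) × 0.01 over 18 periods:
- m = 2,250 / 18 = 125 gives 2.24.
- m = 3,000 / 18 = 166.7 gives 2.66.
- Standard error ratio: √[(2.657/1,000) / (2.24/750)] = 0.943, a 6% reduction.

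Adding washout patients alone (880 per group, m = 146.7, design effect 2.457) gives √(750/880) = 0.923 without clustering, an 8% reduction. With clustering it is √[(2.457/880) / (2.24/750)] = 0.967, a 3% reduction.

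**5. Dilution.** If the added 25% carry a fraction f of the true effect, the expected test statistic changes by (0.75 + 0.25f) / (standard error ratio). With f = 0 and no clustering this is 0.75 / 0.866 = 0.866, a 13% fall. Break-even needs f = (0.866 − 0.75) / 0.25 = 0.46 without clustering, or (0.943 − 0.75) / 0.25 = 0.77 with it.

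**6. Are the safety events recorded throughout?** Protocol 7.3 lists them among electronically extracted daily data for days 0 to 28. Supplement section 18 lists them as manual-only data, reviewed for patients enrolled in the first 12 months. If section 18 governs, patients contributing to a safety comparison in the primary population are about (1 − 0.148)/3 = 28% to (1 − 0.115)/3 = 30% of those enrolled. That year ends before January 2020, where the plan dates the pandemic period, so a COVID-19 row for these events would be empty. It does contain six washouts, whose events would be ascertained and then left out.

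**The case against.** A reader might infer that a quarter of patients treated under an assigned target enter no planned safety comparison. The documents do not support that, for three reasons.

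- **Size.** The 25% subtracts one forecast from another with a different base. Only the washout share can be derived from stated figures.
- **Exposure.** The SAP gives two reasons for excluding COVID-19 patients: possible imbalance between groups, and transfer to a non-participating ICU with little expected exposure to the intervention. The second bears on safety as well as efficacy.
- **No comparison at all.** Death before day 28 scores zero VFDs, so deaths among excluded patients do enter the all-enrolled VFD analysis. The DSMB interim analysis is for efficacy and safety and states no washout exclusion, and the DSMB charter (section 6) allows by-arm safety data in closed session.

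The first two points stand in full. The third stands in part. Within VFDs, a death shares its zero with a patient still ventilated at day 28, so mortality is not separately visible. The interim analysis covers only the first 18 months, hence 9 of the 18 blocks and none of the pandemic period. Confidential DSMB review is also not a reported final comparison.

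The strongest remaining objection is dilution. The assigned target lapses at the end of the block and clinicians then choose (protocol 7.1; supplement section 8), and washout enrollees are the patients most likely to be cut short in this way. Adding them, and briefly exposed COVID-19 patients, can pull a difference toward zero and hide harm. That is a good reason to keep the primary population as the main comparison, but not to omit the all-enrolled one.

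**Conclusion.** The concern holds for the final analysis. Mortality and safety outcomes are compared only in the primary (main) population, and no all-enrolled repeat is planned for them. The clearest gap is the washout group, about 11 to 15% of enrolled patients. The total reaches about 25% only if roughly 10 to 14% of those enrolled had COVID-19, which the documents do not state.

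The gain is mainly completeness of reporting. Standard errors would fall by at most about 13% at an assumed 5% event rate with no clustering, and by about 6% if the 0.01 correlation carries over to safety events. The primary VFD result is unaffected. How far the safety-event part matters depends on whether those events are ascertained throughout the trial or only in year one, which the documents leave in conflict.

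**What to change.** - First reconcile protocol 7.3 with supplement section 18, and state for each safety outcome the period and the patients in whom it is ascertained.
- Extend the planned all-enrolled sensitivity analysis to 28-day in-hospital mortality and to every exploratory safety outcome, in all patients in whom it was ascertained, by target assigned at enrollment. Show washout and COVID-19 patients in separate rows.
- Keep the primary-population comparison as the main one. State that the all-enrolled result is diluted and must not be read alone as evidence of no harm.
- State the expected or actual number of COVID-19 exclusions, so that the excluded share can be calculated.

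The cost is SAP wording and one table. For mortality no new data are needed, since death before discharge is already collected by both manual and automated methods. For safety events the cost depends on the reconciliation: if they were ascertained only in year one, the added rows cover that year alone.
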